6.4.2 Non-intervention Cohort

Infants whose parents decline treatment with timolol will have follow-up office visits at day 30±5 days, 60±5 days, 120±5 days, and 180±5 days.

During the office visits, the following procedures will be performed as specified in Table 6-1:

1. Physical examination, including weight, blood pressure, heart rate.
2. Photographs and measurements of the IH. The treating physician will collect data

- on the clinical characteristics and measure width and thickness of the target hemangioma and perform color and volumetric size VAS assessments.
3. Hemangioma dynamic complication scale for IH that are ulcerated or threaten function
 4. Adverse events/ solicitation of AEs of special interest
 5. Parent Hemangioma QoL screen
 6. Concomitant medications

6.5 Follow-up Period

For treated participants, a follow-up period through day 7 (+5 days) after completing study drug or last study procedure, as applicable, will include solicitation of concomitant medications and assessment of adverse events/AEs of special interest.

For all treated participants that complete 180 days of treatment on study drug, the follow-up period through day 90 (± 5 days) after study drug has been completed, will include solicitation of timolol dosing information and adverse events of special interest.

If a participant's last day of treatment phase ends after day 180 (+5 days) (e.g., out-of-window visit), site staff should continue the follow-up period for the full 90 days post last dose.

Infants who participate in the non-intervention cohort, will have no further follow up beyond 180 days.

6.6 Efficacy Assessment Using Centralized VAS

Efficacy will be determined at the end of the study by centralized evaluation of five standardized digital photographs (taken by investigators at each visit). All collected images from both arms of the study and the untreated control group will be evaluated in a masked fashion by expert pediatric dermatology Raters. Each study site will be given photographic equipment and a minimum of two individuals at each site will be trained to capture standardized photographs. Detailed information will be in the MOP and the photography vendor's User's Manual on how to take the pictures of the infant's hemangioma in order to obtain a systematic and consistent approach. All study and control photographs will undergo a centralized/standardized color calibration by the photography vendor before they are sent for assessment by the Raters. Two expert Raters and one Adjudicator will be trained on the Visual Analog Scale (VAS), how to recognize change in volume and color, and in the comparison of the hemangioma from baseline to study endpoint. However, assessment will initially be completed by 2 of the Raters. Adjudication by the Adjudicator will occur in a case of disagreement between the two Raters (see Rater's User's Manual). For the purpose of this study, a disagreement will be defined as a difference in both Raters' assessment concerning the treatment response categories on the VAS scale. Raters will use the VAS (see Section 10.1) to rate changes in volume and changes in color separately. Raters will be masked to both treatment assignment and timing of the digital photograph. Interreader and intrareader reliability of the Raters will be assessed prior to evaluation of study infants. The scores of the centralized Raters will be used to determine the success or failure of timolol therapy to obtain partial or complete regression of hemangioma in each study infant.

6.7 Laboratory Evaluations

When clinically indicated, investigators will evaluate infants for the presence of hypoglycemia (serum glucose < 60 mg/dL).

6.8 PK Sampling

Parents/guardians of infants in the treated groups will have the option to consent for PK blood draws, heel sticks, or finger sticks. **Refusal to provide consent for the PK portion of the study**

does not preclude involvement in the main study. Infants who have parental/guardian consent for the PK portion of the study will have up to 3 blood samples obtained during the study period and at least one sample should be collected within 2 hours of any dosing. Table 6-2 below outlines optimal sampling periods. Efforts should be made to obtain samples according to the sampling schedule; however, samples obtained outside of the sampling windows will not be considered protocol deviations. Blood pressure and heart rate must be collected within 15 minutes before or after sample collection.

Table 6-2: Optional sampling collection windows (relative to drug application)

Sample option*	Sampling Window
1	Within 2 hours
2	2-4 hours
3	5-7 hours
4	8-10 hours
5	11-12 hours (prior to repeat dose)

* At least one sample should be collected within 2 hours of dosing.

6.8.1 Minimizing Blood Loss

Blood samples will be collected in 250 µL aliquots. To minimize the amount of blood sampling, no more than 3 PK samples (750 µL in total) will be obtained from each infant for analysis.

6.8.2 Specimen Preparation, Handling, and Shipping

Detailed information will be in the MOP.

7 STUDY PRODUCT DESCRIPTION

7.1 Dosage and Study Drug Information

Dosing scheme

Parents/guardians or hospital providers will topically apply 1 drop [approx. 0.05 ml of timolol maleate 0.5% GFS, which is 0.25 mg, or approximately 0.05 ml of timolol maleate 0.25% GFS, which is 0.125 mg] twice daily soon after feeding, to the surface of the hemangioma. The site will remain uncovered unless ulcerated or under the diaper, in which case a bandage will be applied when possible. Parents will record daily dosing in a log. Written instructions on how to apply study drug on the hemangioma will be provided to the parents at time of randomization and/or first study drug dispensing; the study site team (PI or designee) will show the parents how to apply the correct dose (i.e., drop) by applying the first treatment. Detailed instructions will be provided in the MOP. At each visit study drug bottles will be weighed to verify compliance. A discrepancy of >0.75g (+/-) between the expected bottle weight and the actual bottle weight at Visits 02 and 03 will be recorded as a protocol deviation. A bottle weight discrepancy of >1.5g (+/-) at Visits 05 and 07 will be recorded as a protocol deviation. Participants will not be early terminated because of a bottle weight discrepancy or participant non-compliance.

A deviation for participant non-compliance will be recorded if:

A participant has 12 or more missed doses per visit (previous 30 days of the treatment period)

A participant has 72 or more missed doses over the 6-month treatment period

A participant has 4 consecutive missed doses.

7.2 Formulation, Packaging, and Labeling

Any requisite clinical trial materials will be provided with labeling in accordance with all applicable regulatory requirements. Detailed information will be part of the MOP.

7.3 Product Storage and Stability

All investigational products must be stored in a secure area with access limited to the investigator and authorized site staff and under physical conditions that are consistent with investigational product-specific requirements provided by the Sponsor. Detailed information will be part of the MOP.

7.4 Other Medications/Treatments

The following concomitant medications are not permitted during the study:

1. Topical corticosteroids applied to the IH (topical corticosteroids used on areas unaffected by IH are permitted)
2. Oral or intravenous beta blockers
3. Oral or intravenous corticosteroids

All other drugs are permitted while on study.

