5.2.2 Exclusion Criteria

1. History of previous treatment with any pharmacologic or laser therapy for IH
2. Ongoing therapy with an oral beta blocker or oral corticosteroid (e.g., cardiac arrhythmia, adrenal insufficiency, upper airway obstruction, tetralogy of fallot, hypertension, reactive airways disease)
3. IH that requires systemic therapy (defined by dynamic complication scale >3)
4. Infants with more than one hemangioma that requires therapy
5. IH of the non-keratinized mucosa
6. Hemodynamically significant cardiovascular disease, as determined by the investigator
7. Known allergy to beta blockers or vehicle
8. Heart rate <100 beats per minute at screening visit
9. Known prenatal or postnatal diagnosis of 2nd/3rd degree atrioventricular block
10. History of reactive airway disease (RAD)
11. Any condition which would make the participant, in the opinion of the investigator, unsuitable for the study

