5.3.3 Reasons for Participant Withdrawal

5.3.4 Withdrawal from Treatment Phase (study drug dosing)

The clinician or family may choose to suspend study drug dosing for any reason during the study period, and the infant will remain in the study.

If at any time during the study, the treating physician determines that the target hemangioma failed therapy and the IH requires more aggressive surgical or alternate pharmacologic therapy (e.g., oral beta blockers, or oral or topical corticosteroids), the infant may be withdrawn from the Treatment Phase and move into the 7 day safety follow-up period. If the participant continues to participate in the study, they will be followed for safety for 7 days after last study dose, and should continue to return for planned study visit activities including photography of the IH.

If a treating physician chooses to withdraw the participant from the Treatment Phase (i.e. discontinue timolol maleate GFS dosing), the treating physician must immediately report this to the DCRI study PI and Protocol Chairs.

The investigator will withdraw a participant from receiving further study drug if:

1. Any clinically significant adverse event (AE) is deemed by the principal investigator to require discontinuation of study drug.
2. The treating physician determines that the target hemangioma failed therapy and requires alternate pharmacologic, laser or surgical intervention.
3. Participant develops ulceration of the target hemangioma after therapy is initiated.
4. Participant receives oral or intravenous corticosteroids or additional oral, intraocular, or topical beta blockers for treatment of any other conditions.
5. Requested by the NIH, FDA, DMC, or PTN.

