4. Absolute change in hemangioma dynamic complication scale from Day 0 to end of study within each treatment arm.
5. Assess time to partial response by comparing baseline to day 30, day 60, day 120 and day 180 in both treatment arms.
6. Absolute change in IH-QoL score scale from Day 0 to end of study within each treatment arm.

Secondary **safety** endpoints are the rate of serious adverse events and adverse events of special interest (Section 8.1.2) from randomization to Day 180 in infants treated with topical timolol maleate (0.25% and 0.5%) GFS for the treatment of infantile hemangioma.

Exploratory Endpoints:

Exploratory PK endpoints include estimation of PK parameters such as clearance (CL), volume of distribution (V), area under the curve (AUC), and maximum concentration (C_{max}), as possible.

The relationship between different hemangioma characteristics and plasma concentrations may also be described as an exploratory endpoint.

Treatment Failure for Partial Response in Hemangioma Color or Volume

The infant will be considered a treatment failure for the primary endpoint of partial response of VAS-volume or the secondary endpoint of partial response of VAS-color from baseline to Day 180 if any of the following conditions are met:

1. Partial response not achieved at the Day 180 visit in infants who complete the 180-day treatment period.
2. Infant withdrawn from masked treatment due to progressive disease. This will include participants randomized to the 0.25% treatment arm and switched to the 0.5% treatment arm.
3. Ulceration of the target hemangioma after initiation of masked treatment.
4. Infant withdrawn from study treatment due to safety concerns.
5. Study drop-out or loss to follow-up after the 30-day visit and before the 180-day visit for reasons other than progressive disease, ulceration, or safety concerns without having achieved partial response at the last study visit before drop-out.

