17.5 Protocol Deviations

A protocol deviation is any noncompliance with the clinical trial protocol, GCP, or manual of procedures requirements. The noncompliance may be on the part of the participant, the investigator, or the study site staff. As a result of deviations, corrective actions are to be developed by the site and implemented promptly.

These practices are consistent with Good Clinical Practice:

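### Sections 7.4 and 5.3.4 disagree on topical, intraocular and intravenous beta blockers and must be reconciled

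*Combined protocol and SAP*

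**What the plan says.** Section 7.4 has a three-item list of medications not allowed during the study. The beta blocker entry reads "Oral or intravenous beta blockers". The other two entries concern corticosteroids. The section closes with "All other drugs are permitted while on study".

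Section 5.3.4 governs withdrawal from dosing, and its list is mandatory: "The investigator will withdraw a participant from receiving further study drug if" any of five conditions is met. Item 4 is: "Participant receives oral or intravenous corticosteroids or additional oral, intraocular, or topical beta blockers for treatment of any other conditions". The withdrawal is from study drug, not from the study. The same section expects infants who stay in to keep attending visits and having the lesion photographed.

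Section 17.5 defines the consequence of not following either rule: "A protocol deviation is any noncompliance with the clinical trial protocol, GCP, or manual of procedures requirements".

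Section 10.1 lists five conditions that make an infant a treatment failure for the primary endpoint. Two matter here: "Partial response not achieved at the Day 180 visit in infants who complete the 180-day treatment period" and "Infant withdrawn from study treatment due to safety concerns".

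**The concern.** Two sections give opposite instructions for the same event. An infant who starts a topical or intraocular beta blocker for another condition is taking a permitted medication under 7.4 and must come off study drug under 5.3.4. There is no cross-reference and no statement of which section takes precedence.

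The subject is not incidental. Section 2.3.1.2 describes the risks of timolol largely as those of systemic beta blockade, and most of the adverse events of special interest in Section 8.1.2 are its possible effects. Section 2.1 reports substantial systemic absorption of intraocular timolol in adults and serious events in infants given ophthalmic timolol. The routes that 7.4 leaves open are ones that the protocol itself treats as relevant to systemic exposure.

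Three things depend on which section a site follows:

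- **Exposure and safety.** The infant either continues on two sources of beta blocker or stops study drug.
- **Follow-up.** Sections 6.5 and 8.1 tie the 90-day special-interest follow-up to completing 180 days of treatment, although Section 8.1.4 states it for the treatment arm without that condition. Stopping study drug could therefore also shorten follow-up.
- **PK.** If the added drug is timolol, measured concentrations mix two sources. The characteristics named as examples in Section 10.4.5 do not include concomitant beta blocker use.

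**Working it through.** The plan gives no figure on this point, so there is none to reproduce. The sample size and power in Section 10.3 do not enter. The check compares the texts.

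**Step 1: compare the routes.**

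| Beta blocker route | Section 7.4 | Section 5.3.4, item 4 (given for another condition) | Do they agree? |
|---|---|---|---|
| Oral | Barred | Study drug stopped | Yes |
| Intravenous | Barred | Not listed | No: barred, but no stated consequence |
| Intraocular | Not listed, so permitted by the closing sentence | Study drug stopped | No: conflict |
| Topical | Not listed, so permitted by the closing sentence | Study drug stopped | No: conflict |

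One route in four is handled alike. For comparison, oral and intravenous corticosteroids appear in both places with the same routes. That suggests the two lists were meant to correspond.

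**Step 2: follow each rule to its consequence.** Take an infant on study drug who is given an intraocular beta blocker for an eye condition. A site that checks only 7.4 finds nothing prohibited, continues study drug and has nothing to report. A site that checks 5.3.4 stops study drug. Under 5.3.4, the first site's conduct is noncompliance with the protocol and so a deviation by Section 17.5. That sites will in fact differ is an inference, but it follows directly from the two texts.

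**Step 3: classify that infant for the primary endpoint.** Suppose study drug is stopped under item 4 and the infant stays in the study to Day 180. Against the five failure conditions in Section 10.1:

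1. No partial response at Day 180: worded for infants who complete treatment, which this infant did not.
2. Withdrawal for progression: not the reason.
3. Ulceration: not the reason.
4. Withdrawal for safety concerns: arguable, but a concomitant-medication withdrawal is not named.
5. Drop-out or loss to follow-up: the infant has not left the study.

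No condition clearly applies. A favourable Day 180 photograph could be counted as a response, or as a failure under a broad reading of condition 4.

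**Step 4: size.** The documents give no count of infants likely to receive another beta blocker. For the intraocular route, Section 2.2 puts infantile glaucoma at 1 in 50,000. If that rate held among the 100 randomized infants, and glaucoma were the only indication, the expected number would be 100 × 1/50,000 = 0.002. For topical use in another condition there is no figure to work from.

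**The case against.** The strongest reply is that the two sections can both be true: the other drug is allowed, and study drug stops when it is given. That reading is coherent, but no sentence states it, and a site consulting the concomitant-medication section would not be led to 5.3.4. The intravenous mismatch is also weaker than a contradiction, since no section permits that route. Both points soften the inconsistency without removing it.

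A second reply is that the affected group is close to empty. This largely stands. A reader might infer that infants with several lesions will commonly receive topical timolol on a lesion other than the target. The documents do not support that. In Section 5.2.2, exclusion 4 removes infants with more than one hemangioma needing therapy, and exclusion 1 removes those already treated for hemangioma with any drug or laser. What remains is a second lesion that comes to need treatment later, and it is doubtful that this counts as another condition under item 4.

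A reader might also see a contradiction in exclusion 2, which is limited to "Ongoing therapy with an oral beta blocker or oral corticosteroid". It is not one: an eligibility list need not match an on-study list.

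Nor should it be inferred that the other drug would go unrecorded. Table 6-1 collects concomitant medications from baseline to the contact 7 days after treatment, phone contacts included. What could differ is whether study drug continues and whether a deviation is reported.

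Finally, the gap in Section 10.1 is not created by the clash between 7.4 and 5.3.4. It affects any infant who stops study drug for an unlisted reason and stays in the study, for example when a family suspends dosing. Using the Day 180 outcome regardless of stopping can be a legitimate choice in an intent-to-treat analysis. That is fair, but the choice has to be stated.

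**Conclusion.** The inconsistency is real. Topical and intraocular beta blockers are permitted by 7.4 through its closing sentence, yet require study drug to stop under 5.3.4 when given for another condition. Intravenous beta blockers are barred by 7.4 but are not a trigger in 5.3.4. The finding rests on the wording alone and on the absence of any precedence rule.

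The number of affected infants is unknown and probably very small. With 45 evaluable infants per arm, one infant reclassified moves a response proportion by 1/45, or 2.2 percentage points, and a reader might infer a threat to the primary result. The documents do not support that: the figure is what any single infant contributes, and without a count it shows no material effect.

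The point still warrants correction, because the conflicting rules concern added beta blocker exposure in young infants and the correction is cheap.

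**What to change.** 1. The sponsor must reconcile Sections 7.4 and 5.3.4, item 4, so that the beta blocker routes and drug classes agree and each section refers to the other. Which rule is right is for the sponsor to decide.
2. In Section 10.1, state how an infant who is taken off study drug under item 4 and remains in the study is classified for the primary endpoint.
3. In the analysis, derive a flag for concomitant beta blocker use by any route and list the flagged infants in the safety and PK outputs. With so few expected, a listing is enough; repeating the analyses without them is not needed.

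The cost is protocol wording, one sentence in the endpoint definition and one variable derived from medication data already collected. No visit, assessment or change in sample size is needed.

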8 ASSESSMENT OF SAFETY

8.1 Methods and Timing for Assessing, Recording and Analyzing Safety Parameters

Safety will be assessed in all infants following initial study-specific procedure through 7 days (+5 days) post last study dose or last study procedure, as applicable, and will be assessed by frequency and incidence of AEs and SAEs. Those outpatient infants whose parents are willing and able to remain in clinic for a period of 2 hours after the initial application of timolol will also have vital signs (heart rate and blood pressure) collected at 1 hour and 2 hours (+/- 15 mins). The infant will be monitored for signs and symptoms of an AE or AE of special interest during this period, particularly bronchospasm, arrhythmias, and hypoglycemia.

Inpatient infants will be monitored by hospital staff. Hospital staff will collect vital signs (heart rate and blood pressure) 1 and 2 hours after the initial application of timolol and monitor for signs of an AE or AE of special interest during this period.

For all treated participants that complete 180 days of treatment on study drug, the follow-up period through day 90 (± 5 days) after study-specific drug has been completed will include solicitation of adverse events of special interest only. Infants whose parents decline treatment with timolol will have no further follow up beyond 180 days. Refer to Figure 1 and Table 6-1. A safety monitoring committee (DMC) will be convened by NIH to review data and safety information from study infants throughout the study.

8.1.1 Adverse Event

An **adverse event** (AE) is any untoward medical occurrence in humans, whether or not considered drug-related, which occurs during the conduct of a clinical trial. (Any change in clinical status, routine labs, x-rays, physical examinations, etc.), that is considered clinically significant by the study investigator is considered an AE.

Suspected adverse reaction is any adverse event for which there is a reasonable possibility that the drug caused the adverse event. A reasonable possibility implies that there is evidence that the drug caused the event.

Adverse reaction is any adverse event caused by the drug.

Serious adverse event or **serious suspected adverse reaction** or **serious adverse reaction** as determined by the investigator or the sponsor is any event that results in any of the following outcomes:

1. Death
2. Life-threatening AE ("life-threatening" means that the study participant was, in the opinion of the investigator or sponsor, at immediate risk of death from the reaction as it occurred and required immediate intervention)
3. Persistent or significant incapacity or substantial disruption of the ability to conduct normal life functions
4. Inpatient hospitalization or prolongation of existing hospitalization
5. Important medical event that may not result in one of the above outcomes, but may jeopardize the health of the study participant or require medical or surgical intervention to prevent one of the outcomes listed in the above definition of serious event

